7.6. Data Management

CRF data collected by the investigator will be entered into the clinical database. Validation will be performed after comparison of the double data entry. All missing data or data for review will be reported on a query sheet for further validation at the study site. Any data modifications will be recorded.

Adverse events will be coded using the World Health Organization - Adverse Reaction Terminology. Medical history will be coded using the classification of the Statistics Korea, and concomitant drugs coded using www.kimsonline.co.kr provided by KIMS Co. Ltd.

Statistical analysis will be carried out using SAS software version 9.2 or above.

7.7. Data Analysis

7.7.1. Evaluation parameters

1) Case parameters

- Descriptive analysis will be performed regarding the total number of collected CRFs, the number of safety evaluation subjects, the number of efficacy evaluation subjects, the number of discontinued cases and their reasons.

2) Safety parameters

- Safety parameters will be evaluated.
- The incidence of adverse events sorted by body organ and disease/symptom
- If the data is adequate, sub-analysis can be performed for each factor that is considered to affect safety.
- Clinically significant abnormalities found in laboratory tests (if conducted)

3) Efficacy variables

- On-demand treatment
 - Responses to all the injection of the Xyntha Solofuse prefilled syringe used to treat bleeding (4 point scale: excellent, good, moderate, and no response)
 - Number of observations of less than expected therapeutic effect (LETE) (LETE: “no response” rated after each infusion of 2 consecutive infusions within 24 hours after on-demand treatment)
 - In case of bleeding: The number of infusions of Xyntha Solofuse prefilled syringes used to treat each new bleeding episode is rated.
 - Mean infusion dosage
- Prophylactic Therapy
 - Percentage of the study subjects who have experienced bleeding (overall, spontaneous)
 - Annualized bleeding rates (ABRs)
 - Number of observations of less than expected therapeutic effect (LETE)

(LETE: Atypical bleeding occurring within 48 hours after administration of the Xyntha Solofuse Prefilled Syringe by dosage for the prevention of bleeding (spontaneous/at traumatic))

- Mean infusion dosage
- Total factor consumption
- If the data are adequate, sub-analysis can be performed for each factor that is considered to affect the efficacy.

7.7.2.1. Safety Analysis

- Number and incidence of adverse events sorted by body organ, disease/symptom
- If the data are adequate, the Chi-square test (X^2 -test) or the Fisher's exact test can be used for subgroup analysis.

If necessary and if the data are adequate, the pairwise comparison and/or the descriptive analysis method will be used for clinically significant abnormalities found in the laboratory tests that have been reported as adverse events.

7.7.2.2. Efficacy Analysis

A descriptive summary will be performed for efficacy endpoints.

Details about the summary and statistical analysis of the data collected in this study will be included in the statistical analysis plan (SAP), and the sponsor will date, organize and retain the SAP. The plan described in the protocol may be amended in the SAP. The definition of the primary endpoint, or important revisions to the analysis will be reflected in the protocol amendment.

CCI

7.9. Strength and Limitations of the Study Methods

Strength:

- This is a non-interventional study to observe the safety and efficacy of the study drug under the actual condition of use.

Limitations:

- This is a study mandated by the regulatory authority to maintain approval.
- SAP and the number of study subjects to be enrolled will be decided, not by specific diseases and/or characteristics of the drug, but by the guidelines for the re-examination of new drugs etc. by the Ministry of Food and Drug Safety.

7.10. Other Aspects

Not applicable

8. PROTECTION OF HUMAN SUBJECTS

8.1. Subject information and consent

Although the written consent form (for the use of personal information) does not need to be obtained due to the unidentifiable records collected in this study, all the parties guarantee the protection of personal information of the study subjects, and the names of the subjects shall not be included in any Pfizer forms, reports, publications, or other public materials except when the law requires. For the delivery of materials, Pfizer will maintain the highest level of confidentiality and protection of the study subjects' personal information.

8.2. Subject Withdrawal

Not applicable

8.3. Institutional Review Board (IRB)/Independent Ethics Committee (IEC)

The study protocol will be submitted to the MFDS prior to the study. The ethical consideration in this study will be evaluated by the IRB/IEC in each study site prior to the study, if the site has the approval procedures for the PMS study according to the standard operating procedure of each study site.

It is the responsibility of the investigator to obtain prospective approval for the study protocol, protocol amendments, and other relevant documents, if applicable, by the IRB/IEC. All correspondences with the IRB/IEC should be retained in the investigator file. The copy of the IRB/IEC approval letters should be forwarded to Pfizer or the Pfizer representative.

8.4. Ethical Conduct of the Study

This study will be conducted in accordance with the legal and regulatory requirements, scientific purpose, value and rigor, and will follow the generally accepted research practices described in the guidelines for Good Pharmacoepidemiology Practices (GPP) issued by the International Society for Pharmacoepidemiology (ISPE), Good Epidemiological Practice guidelines issued by the International Epidemiological Association (IEA), Pharmaceutical Research and Manufacturers Association (PhRMA) guidelines, and Korea PMS regulations and/or guidelines.

9. MANAGEMENT AND REPORTING OF ADVERSE EVENTS/ADVERSE DRUG REACTIONS

This study generally uses the existing medical database that is unlikely to connect a particular product to medical incidents of an individual (in other words, to identify potential connections).

Also, this study protocol requires the review of unstructured data at the level of the study subjects. Unstructured data refer to original medical materials including text-centered

explanations and medical records, descriptive images from the doctor, visual explanations on medical information such as a nerve scan, X-ray or the description section of the database. The reviewer is responsible for reporting all adverse events, which appear in the reviewed information (as defined by the study period and subject group specified in the protocol), clearly attributed to Pfizer products. Clear attribution is not inferred from the temporal relationship between drug administration and adverse events, but should be based on the clear causal statement of the medical provider, which connects drug administration and adverse events.

The requirements for reporting safety incidents using the non-interventional study (NIS) adverse event monitoring (AEM) report form to Pfizer Safety are as follows:

- All serious adverse events and non-serious adverse events, which appear in the reviewed information, clearly attributed to all Pfizer drugs should be recorded in the case report form, and should be reported using the NIS AEM report form to Pfizer Safety within 24 hours of recognition.
- Scenarios related to drug exposure such as exposure during pregnancy, exposure during breastfeeding, medication errors, overdose, misuse, extravasation, lack of efficacy and occupational exposure related to the use of Pfizer products should be reported within 24 hours to Pfizer Safety using the NIS AEM report form.

For these safety incidents clearly attributed or related to the use of Pfizer products, the data collected in the medical record constitute all clinical information known to be related to such adverse events. No follow-ups are conducted for relevant adverse events.

All the study staff will complete “*Your Responsibility for Reporting: Safety, Performance and Quality Monitoring of Pfizer Products (in multiple languages)*” and the Pfizer requirement for supplementary training on their responsibility to report. These trainings are provided for all the study staff before the start of the study. For all training, training completion records include the “Certificate of Training Completion” (signed by the attendee) and should be kept in the retrievable form. The copy of all signed certificates of training completion should be offered to Pfizer.

10. PLANS FOR DISSEMINATING AND COMMUNICATING STUDY RESULTS

For the first 2 years, 6-month reports are submitted to the MFDS (i.e. Reports 1-1, 1-2, 2-1, and 2-2). Thereafter, data collected in the 3rd year are reported to the MFDS annually. The final study report (i.e. re-examination report) is submitted to the MFDS in the 4th year, including all data collected during the entire study period (see Section 4).

COMMUNICATION OF ISSUES

In the event of any prohibition or restriction imposed (e.g. clinical hold) by an applicable jurisdictional authority in each region of the world, or if the investigator becomes aware of any new information which may influence the evaluation of the benefits and risks of the Xyntha Solofuse prefilled syringe, it should be reported to Pfizer immediately.

In addition, the investigator must inform Pfizer immediately of any urgent safety measures taken by the investigator to protect the subjects against any immediate hazard, and of any serious breaches of this non-interventional study protocol that the investigator becomes aware of.

ANNEX 1. LIST OF STAND ALONE DOCUMENTS

None

ANNEX 2. ADDITIONAL INFORMATION

Not applicable

Xyntha Solofuse prefilled syringe was approved on March 31, 2014 in Korea. The Xyntha Solofuse prefilled syringe is administered by intravenous infusion after reconstitution of the freeze-dried powder with the diluent (0.9% Sodium Chloride). This drug consists of the identical ingredients with the previous Xyntha injection, and the drug and the diluent are supplied within the prefilled dual-chamber syringe. As required for all new drugs approved by the Ministry of Food and Drug Safety (MFDS), information on the safety and efficacy of the new drug should be provided based on the study conducted with at least 600 study subjects who are administered this drug in the setting of routine practice for 4 years from the approval date (March 31, 2014 - March 30, 2018). This non-interventional post-marketing surveillance (PMS) study is an obligation to the MFDS. Although 600 is the assigned number of study subjects, the number of cases will be adjusted considering the actual number of enrolled subjects after the study start day. Background information on Xyntha Solofuse prefilled syringe can be obtained from the current version of the local product document, which is the single reference safety document (SRSD) for information relating to the Xyntha Solofuse prefilled syringe in this study.

2. Study objective(s) and Others

2.1. Objectives

This study aims to observe the safety and efficacy of the Xyntha Solofuse prefilled syringe in the setting of routine practice. The primary objective is to detect medically significant events (factor VIII inhibitor). The secondary objective is to observe the overall efficacy and safety of the Xyntha Solofuse prefilled syringe including serious adverse events.

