4.6. Safety Endpoints

- 1) The incidence and number with 95% confidence Interval for all adverse events/adverse drug reactions investigated within 6 months from initial administration after at least 1 dose of Xyntha solofuse prefilled syringe (If the study subject has not completed the 6-month treatment, relevant data should be collected based on the medical records within the 30 days after the last administration of the drug)

- ① Severity
- ② Action taken
- ③ Seriousness
- ④ Outcome
- ⑤ Causality assessment

2) Laboratory Test

- ① Blood test(Hemoglobin, Hematocrit, RBC, WBC, Platelet Count, ESR, CRP)
- ② Biochemical test(AST(SGOT), ALT(SGPT), ALP, BUN, Creatinine, Factor VIII Inhibition Factor Hemoglobin)
- ③ Urine examination(Protein/Albumin, Glucose/Sugar, Hemoglobin/Blood)

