5.1. Analysis Principles

Statistical analysis will be conducted after database is locked and performed using SAS software version 9.4 according to this statistical analysis plan. If statistical analysis methods are changed, it will be described in the final study report.

Continuous variables will be summarized by the descriptive statistics (n, mean, median, SD (standard deviation), minimum, and maximum). Categorical variables will be presented in the frequency distribution table (n, %).

In case of statistical hypothesis testing, two-sided test will be conducted under 5% significance level and the p-value of each test result will be presented in the summary table.

6. Statistical Analyses

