6.6. Safety Analyses

Safety analysis will be performed based on data of safety analysis set. All adverse events in CRF will be classified by System Organ Class (SOC) and Preferred Term (PT) according to the Korean 092 Version of WHO-ART distributed by Korean Ministry of Health and Welfare.

- 1) All adverse events occurred during or after administration of this medicinal product will be summarized by frequency and percentage (n, percentage) by categorizing as follows. Also, it will be presented in n, incidence proportion, 95% confidence interval of incidence proportion and number of events for each SOC and PT.
 - ① Frequency analysis of adverse event/adverse drug reaction
 - ② Frequency analysis of serious adverse event/serious adverse drug reaction
 - ③ Frequency analysis of unexpected adverse event/unexpected adverse drug reaction
- 2) All adverse events by categorizing as follows will be presented in number of events and percentage.
 - ① Occurrence status of adverse event and adverse drug reaction by its severity
 - Mild
 - Moderate
 - Severe
 - ② Occurrence status of adverse event and adverse drug reaction by its action taken related with administrating this medicinal product.
 - No change
 - Dosage reduced
 - Dosage increased
 - Temporarily discontinued
 - Permanently discontinued
 - Not applicable
 - ③ Occurrence status of adverse event and adverse drug reaction by other action taken
 - Therapeutic prescription
 - Other
 - No treatment
 - ④ Occurrence status of adverse event and adverse drug reaction by its seriousness
 - If a death is caused;
 - If it is life-threatening (risk of an immediate death);
 - If hospitalization or extended duration of hospitalization is required;
 - If persistent or significant disability or malfunction is induced (substantial disruption in the ability to conduct normal life functions);
 - If congenital anomalies/birth defects are induced.

Statistical Analysis Plan for rPMS

- Important medical event: if it is determined that the event may jeopardize the patient or may require intervention to prevent one of the other outcomes listed in the definition above
- ⑤ Incidence of adverse event and adverse drug reaction by outcome
- Yes
 - Unknown
 - No (disappeared)
- ⑥ Occurrence status of adverse event and adverse drug reaction by its causality assessment.
- Related to this medicinal product:
 - I. Certain
 - II. Probable/likely
 - III. Possible
 - V. Conditional/unclassified
 - VI. Unassessable/unclassifiable

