 - Not related to this medicinal product:
 - IV. Unlikely
- 3) Occurrence status of adverse event by demographics and baseline characteristics
- Occurrence status of adverse events will be presented in frequency and percentage and incidence proportion with 95% confidence interval based on categorical variables of demography and baseline characteristics of the patients (sex, age group, past/present disease status, renal/hepatic disorder status). To identify statistically significant difference in occurrence of adverse events among demography and baseline characteristics, Chi-square test or Fisher's exact test will be performed.
- 4) Occurrence status of adverse event by concomitant treatment/therapy
- Occurrence of adverse events will be presented in frequency and percentage and incidence proportion of adverse events with 95% confidence interval by concomitant treatment status and concomitant therapy status. To identify statistically significant difference in occurrence of adverse events among concomitant treatment status, concomitant therapy status, Chi-square test or Fisher's exact test will be performed.
- 5) Analysis of factors that affect safety
- Logistic regression analysis will be performed and an odds ratio with 95% confidence interval will be presented to identify the factors that affect occurrence of adverse events in demography and baseline characteristics (sex, age group, past/present disease status, renal/hepatic disorder status), or concomitant treatment status, concomitant therapy status, etc.

Statistical Analysis Plan for rPMS

- 6) Test of difference for laboratory data before and after administration.
Laboratory data before and after administration will be presented by descriptive statistics and test of difference for laboratory data before and after administration will be performed by using paired t-test (or Wilcoxon signed-rank test). This analysis will be performed if possible.
- 7) Distribution for special patient populations (children (age<19), elderly (age≥65), renal disorder, hepatic disorder, pregnant woman) will be presented. Also, adverse events and adverse drug reactions collected by these groups will be presented in incidence proportion and number events of it for each SOC and PT.

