- 8) Distribution for subgroups status (patients with prior treatment experience/patients with prior non-treatment experience) will be presented. Also, adverse events and adverse drug reactions collected by these groups will be presented in incidence proportion and number events of it for each SOC and PT.
- 9) Distribution for excluded safety patient groups will be presented. Also, adverse events and adverse drug reactions collected for these groups will be presented in incidence proportion and number events of it for each SOC and PT.

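### Detecting factor VIII inhibitors is the primary objective, but the plan designates no primary inhibitor endpoint, does not define an on-treatment case and sets no tested denominator; separately, its enrolment figure of 600 conflicts with the expected 95

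*SAP*

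**What the plan says.** **Objective.** SAP 2.1, matching Protocol 6: "The primary objective is to detect medically significant events (factor VIII inhibitor"). Protocol 7.7.2.2 adds that "The definition of the primary endpoint, or important revisions to the analysis will be reflected in the protocol amendment", but neither document names a primary endpoint.

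**How the SAP reaches inhibitors.**
- SAP 4.6 includes the assay in its biochemistry list, run together with another item: "ALP, BUN, Creatinine, Factor VIII Inhibition Factor Hemoglobin".
- SAP 6.6 item 6 covers all laboratory items: "Laboratory data before and after administration will be presented by descriptive statistics and test of difference for laboratory data before and after administration", by paired t-test or Wilcoxon signed-rank test. It adds: "This analysis will be performed if possible". SAP 5.1 gives the general summary: "Continuous variables will be summarized by the descriptive statistics (n, mean, median, SD (standard deviation), minimum, and maximum").
- SAP 6.6 item 1 covers all adverse events in the safety set: "it will be presented in n, incidence proportion, 95% confidence interval of incidence proportion and number of events for each SOC and PT".
- SAP 6.6 item 8 repeats adverse-event incidence by prior treatment, without a confidence interval: "Distribution for subgroups status (patients with prior treatment experience/patients with prior non-treatment experience) will be presented".

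**Testing.** Protocol 7.3.2.4 makes laboratory tests optional. The case report form marks tests as done or not done. It then asks whether there was a clinically significant change after dosing, with an answer option for no test while on the drug.

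**Inhibitor wording.** The only titer threshold is in exclusion criterion 4 (Protocol 7.2.2, SAP 2.3.2). Protocol 7.7.2 repeats it as an analysis exclusion, and SAP 3.1 item 2 removes anyone failing the criteria from the safety set.

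**Size.** Protocol 7.5 and SAP 2.4 give a minimum enrolment of 600. The next sentence but none further on in Protocol 7.5 speaks of more than 86 subjects from 14 sites. Protocol 5 expects about 95 recruited and at least 86 with data after analysis exclusions. The SAP introduction and SAP 2.4 say that 600 will be adjusted and give no replacement.

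**The concern.** A primary objective of detection, even a purely descriptive one, needs three things: what counts as a case, who could have been found to be a case, and a table that puts one over the other. The plan settles none of them for inhibitors.

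An inhibitor reaches the adverse-event table only if it was found, reported and coded as an adverse event. Subjects who never had a post-dose inhibitor test stay in the denominator as event-free. The laboratory route summarises a change in values and does not give the number who became positive.

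Criterion 4 adds a second risk. Its titer clause takes in results in the laboratory's normal range as well as those of 0.6 BU/mL or more. It allows a clinical judgement where no test can be done, and it sets no time point for current or suspected inhibitors. Because it also serves as an analysis exclusion, the target event could itself become a reason for removal.

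At stake is whether a report of no inhibitors, or few, can be interpreted. The size wording matters less, but the SAP gives a reader no figure from which to judge what the study can exclude.

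**Working it through.** **1. The stated size.** The documents give no calculation behind 600, so it cannot be re-derived; they say that a sample size calculation does not apply. The two smaller figures agree with each other: 86/95 = 0.905, or 9.5% excluded, and with an assumed 10% exclusion 95 × 0.90 = 85.5, which rounds to 86. The 600 does not fit either: 600/95 = 6.3 and 600/86 = 7.0. Exclusions or rounding cannot bridge that gap.

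**2. What zero cases would exclude.** The exact (Clopper-Pearson) two-sided 95% upper limit for 0 of n is 1 − 0.025^(1/n).

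| n | Source | Upper limit |
|---|---|---|
| 95 | Protocol 5, enrolled | 3.81% |
| 86 | Protocol 5, with data | 4.20% |
| 60 | assumed number tested | 5.96% |
| 43 | assumed number tested (half of 86) | 8.22% |

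**3. What two cases would look like.** The count of two is an illustration.

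| Denominator | Proportion | Exact 95% CI |
|---|---|---|
| 86, all with data | 2/86 = 2.3% | 0.28% to 8.15% |
| 60, tested (assumed) | 2/60 = 3.3% | 0.41% to 11.53% |
| 43, tested (assumed) | 2/43 = 4.7% | 0.57% to 15.81% |

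The same two cases read as 2.3% or 4.7% depending on a denominator that the plan does not set.

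**4. Direction of bias.** Suppose incidence is the same in tested and untested subjects and untested cases go unseen. The all-treated proportion is then too low by the factor (number tested)/86: 60/86 = 0.70 or 43/86 = 0.50. If suspicion prompts testing, the tested-only proportion is instead too high. Neither denominator is safe alone.

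**5. The paired test.** If subjects without an inhibitor show no change, the signed-rank test drops them. With k converters, all rising, the exact two-sided p-value is 2 × (1/2)^k. For k = 2 this is 0.50. For k = 5 it is 0.0625, and for k = 6 it is 0.031. Two new inhibitors would therefore read as no significant change.

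**6. Criterion 4 read literally.** Protocol 7.7.2 excludes from analysis subjects who currently have, or are suspected of having, inhibitors. SAP 3.1 item 2 does the same through the eligibility criteria. Neither limits this to status before the first dose. If both cases in step 3 were removed on that reading, the safety set would show 0/84, with upper limit 1 − 0.025^(1/84) = 4.30%. The two cases would appear only among excluded subjects (SAP 3.4 and 6.6 item 9).

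**The case against.** The strongest reply is that this is descriptive, retrospective surveillance and that inhibitors are already covered. SAP 4.6 lists the assay among the safety endpoints. SAP 6.6 item 1 would give a count, a proportion and a 95% CI for an inhibitor reported as an adverse event, and item 8 would give incidence by prior treatment. Because subjects with an inhibitor history are excluded, such an event is in principle a new one. Protocol 7.7.1 and 7.7.2.1 also cover clinically significant laboratory abnormalities. Lack of efficacy counts as an adverse event, so an untested subject is not wholly unobserved. All of this stands. A reader might infer that inhibitors go unanalysed, and the documents do not support that. What is missing is a designated endpoint, a case definition and a tested denominator.

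A reader might also infer that the number tested cannot be recovered, since one line of Protocol 7.3.2.4 asks for items with abnormal values. That goes too far. The same section has fields for tested, not tested and not tested while on the drug, and Protocol 7.2.5.1 lists inhibitors among the laboratory tests without restricting them to abnormal results. The open points are whether these fields are kept for the inhibitor assay itself, and that no planned analysis uses them.

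On criterion 4, an excluded case would still be described under SAP 3.4 and 6.6 item 9, so it would not vanish. It would, however, be missing from the safety-set proportion.

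The Protocol 7.7.2.2 sentence on a primary endpoint is weak evidence: it sits in the efficacy section and concerns where revisions are recorded.

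**Conclusion.** The concern holds and should be fixed. The plan has generic routes to an inhibitor count but no designated primary endpoint, no definition of an on-treatment case and no analysis using the number tested. As written, the adverse-event proportion may understate inhibitor incidence. By how much is unknown, because the documents give neither the share tested nor an expected incidence. The tested numbers 60 and 43 and the two cases are assumptions that show the range.

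The figure that rests on the documents alone is the precision at the expected size: no inhibitors among 86 leaves an upper limit of 4.2%.

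The size conflict is real but minor. A reader might infer that the study loses much of its planned ability to detect inhibitors by falling from 600 to 86. The documents do not support that. The 600 is a regulatory number with no calculation behind it, the SAP says it will be adjusted, and Protocol 5 and 7.5 already describe the smaller study. It is leftover wording that needs correcting.

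**What to change.** 1. **Add one primary inhibitor table to SAP 6.6.** Show the number with a post-dose inhibitor test, the number untested, the number with a new inhibitor, and the proportion with exact 95% CI on both the tested and the all-treated denominators. Give it overall and by prior treatment, and state the direction of possible bias of each denominator. Take the number tested from the Protocol 7.3.2.4 fields if they are recorded for the inhibitor assay; otherwise report it as unknown.
2. **State one case definition for that table,** including how inhibitors judged clinically without a test are counted. Reconcile the criterion 4 wording across Protocol 7.2.2, Protocol 7.7.2 and SAP 2.3.2, and state whether it refers only to status before the first dose, so that on-treatment cases are counted in the primary table.
3. **Add an inhibitor listing or negative/positive shift table** alongside the generic paired test.
4. **Restate the size** in Protocol 7.5, the SAP introduction and SAP 2.4 as about 95 enrolled and at least 86 evaluable. Keep 600 only as the original regulatory number, and give the precision (0/86: upper limit 4.2%).

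**Cost.** Wording in both documents, one extra table with a small listing or shift table, and a less favourable stated size and precision. Planned data collection ended on 30 September 2017, so existing inhibitor results might need re-abstraction at up to 14 sites. Reporting the number tested as unknown avoids that, at the price of having no tested-only proportion.
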